[figure not shown]

## List of Abbreviations and Definitions of Terms

ACR	American College of Radiology
AE	Adverse Event
ANOVA	Analysis of Variance
AUC	Area Under the Curve
BI-RADS	Breast Imaging-Reporting and Data System
CDU	Conventional Diagnostic Ultrasound
eCRF	Electronic Case Report Form
EDC	Electronic Data Capture System
FDA	Food and Drug Administration
GEE	Generalized Estimating Equations
ICF	Informed Consent Form
ICH	International Conference on Harmonisation
IRB	Institutional Review Board
ITD	Intention-to-Diagnose
IUS	Imagio Internal Ultrasound
MRMC	Multi-reader, multi-case
N/A	Not Applicable
NLR	Negative Likelihood Ratio
NPV	Negative Predictive Value
NSR	Non-significant Risk
OA	Opto-Acoustic
PDU	Positive Diagnostic Ultrasound
PDUNB	Positive Diagnostic Ultrasound, No Biopsy
PIONEER	Abbreviated name of a previous study (Pivotal study of Imaging with Opto-acoustics to diagnose breast masses detected by mammography and/or clinical findings: A NEW Evaluation Tool for Radiologists)
PLR	Positive Likelihood Ratio
PMA	Premarket Approval
POM	Probability of Malignancy
PPV	Positive Predictive Value
QC	Quality Control
ROC	Receiver Operating Characteristic
SADE	Serious Adverse Device Effect
SAE	Serious Adverse Event

SAP	Statistical Analysis Plan
SOP	Standard Operating Procedure
USA	United States of America

## **CLINICAL RESEARCH ORGANIZATIONS**

American College of Radiology Center for Research and Innovation (ACR - CRI) will serve as the Imaging Core Lab to conduct the Imagio Feasibility Reader Study. ACR-CRI is located in Philadelphia, PA 19103. ACR-CRI complies with Good Clinical Practices (GCPs) and Title 21 Code of Federal Regulations (CFR) Part 11.

Boston Biostatistics Research Foundation (BBRF) will provide study design, mass sampling, database construction, and data analyses for the Imagio Feasibility Study. BBRF is located in Framingham, MA.

## 1. STUDY OBJECTIVES

### 1.1 Primary Objective

1. To select the effectiveness endpoints and determine the corresponding sample size required for the Pivotal study.
2. To evaluate the gain in *Imagio (Imagio Internal Ultrasound [IUS] + Opto-acoustic [OA])* specificity versus IUS, controlling for sensitivity

### 1.2 Secondary Objectives

To evaluate the following overall and for individual readers for IUS versus Imagio (OA+IUS):

- the Imagio (IUS+OA) partial Receiver Operator Characteristic (ROC) Area under the Curve (AUC) for 95-99% vs IUS for 95-99% sensitivity
- the sensitivity and specificity for Imagio (IUS+OA) versus IUS according to multiple models for readers and masses used for assessing sources of variation
- the Negative Likelihood Ratio (NLR) for IUS versus Imagio (IUS+OA).
- the Imagio (IUS+OA) downgrades and upgrades relative to IUS, separately, for benign and malignant masses
- the net gain (new True Positives [TP] + new True Negatives [TN] – new False Positives [FP] – new False Negatives [FN]) estimate of Imagio (IUS+OA) versus IUS combining benign and malignant masses
- the usage and performance of the SenoGram model for the purposes of determining whether it will be adjusted prior to starting the pivotal study

### 1.3 Other Objectives

To evaluate the following overall and for individual readers for IUS versus Imagio (IUS+OA):

- the differentiation between benign versus malignant masses with respect to Imagio (IUS+OA) feature scores

## 2. ENDPOINTS - endpoints to include a separate mammogram analysis

### 2.1 Primary Endpoint

To evaluate the following overall and for individual readers for IUS versus Imagio (IUS+OA):

- the gain in Imagio (IUS+OA) specificity versus IUS for fixed sensitivity (e.g., 98%) with specificities interpolated from the respective ROC curve as applicable.

## 2.2 Secondary Endpoints

To evaluate the following overall and for individual readers for:

1. the partial ROC AUC corresponding to 95-99% sensitivity with specificities extrapolated from the respective Imagio and IUS ROC curves as applicable.
  - the observed and model-adjusted specificity and sensitivity
  - the Negative Likelihood Ratio (NLR) defined as  $((1-\text{sensitivity})/\text{specificity})$
  - the upgrade and downgrade metrics:
    - the percent correct of downgrades for benign masses from IUS BI-RADS 4a to Imagio (IUS+OA) BI-RADS 2-3, and from IUS BI-RADS 3 to Imagio (IUS+OA) BI-RADS 2
    - the percent incorrect of upgrades for benign masses from IUS BI-RADS 2-3 to Imagio (IUS+OA) BI-RADS 4-5 and from IUS BI-RADS 2 to Imagio (IUS+OA) BI-RADS 3-4-5
    - the percent of incorrect downgrades for malignant masses from IUS BI-RADS 4-5 to Imagio (IUS+OA) BI-RADS 2-3; and
    - the percent of correct upgrades for malignant masses from IUS BI-RADS 2-3 to Imagio (IUS+OA) BI-RADS 4-5.
2. the Cumulative effect of downgrades and upgrades for combined benign masses and malignant masses.
3. the SenoGram usage:
  - Utilization percent reported by the readers
  - Sensitivity and specificity discordance with Imagio (IUS+OA) Downgrades and upgrades versus Imagio (IUS+OA) and IUS, separately for benign and malignant masses
  - POM paired differences versus Imagio (IUS+OA) and IUS, separately for benign and malignant masses.
4. the SenoGram performance:
  - Sensitivity and specificity compared to sensitivity and specificity estimated from cross-validation and hold-out validation.
  - Partial AUC for individual users and overall corresponding to 95-99% sensitivity
  - Separate assessment of Senogram performance with and without mammographic data input.

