**Table 1: Upgrades and Downgrades**

	Imagio (IUS+OA) Clinical Significance Criteria	Imagio (IUS+OA) Statistical Significance Criteria
Benign + TPB Downgrades	BR4a→BR2-3; BR3→BR2	Establish an advantage
Benign + TPB Upgrades	BR2-3→BR4-5; BR2→BR3-4-5	Rule out a disadvantage
Malignant Upgrades	BR2→BR4-5; BR3→BR4-5	Establish an advantage
Malignant Downgrades	BR4→BR2-3; BR5→BR2-3	Rule out a disadvantage

Supporting descriptive statistics will be computed as follows for the correct downgrades and incorrect upgrades for benign masses. Refer to Table 2 below.

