1.1.7.1. Feasibility Analysis Methodology

Data Analyses

Hypotheses generating analyses will be based on independent readers for POM, BI-RADS and feature scores (IUS, IUS+OA pre, IUS+OA post) individually and overall. There are no formal hypothesis tests; p-values from all analyses are descriptive only. There are no adjustments for multiple testing. There will be no adjustment in p-values reported for the planned interim analysis after a minimum of 72 reads by each reader in Cohort 1. Truth (determination of malignant biopsy, benign biopsy, or TPB) will be taken from PIONEER.

The analyses below will be done for Cohort 1, repeated for malignant masses only for cohort 2. No summaries (listings only) will be done for the 5 masses in Cohort 3.

The specificity advantage of IUS+OA post vs IUS, IUS+OA pre vs IUS and IUS+OA post vs IUS+OA pre will be compared at fixed 98% sensitivity. The software package OR-DBM MRMC [Version 2.5 or later] will be used for this analysis of OA gain as interpolated from the ROC curves.

Specificity and sensitivity will be calculated by reader and overall for IUS, IUS+OA pre, IUS+OA post, and the 3 pairwise differences [PROC GENMOD, readers as independent,

repeated as masses as independent]. Specificity and sensitivity will be calculated (not model-adjusted) using the 2% POM cutoff for IUS+OA pre, IUS+OA post and IUS; and then for robustness analyses, for 1%, 3%, 4%, and 5% cutoffs.

Clinically relevant up and downgrades based on BI-RADs are defined as:

- Downgrades: IUS in BR 4a and IUS+OA post in BR 2-3 or IUS in BR 3 and IUS+OA post in BR 2
- Upgrades: IUS in BR 2 and IUS+OA post in BR 3-5 or IUS in BR 3 and IUS+OA post in BR 4-5.

These definitions likewise hold for differences for IUS vs IUS+OA pre and IUS+OA pre and IUS+OA post. These clinically relevant up and downgrades will be reported by reader and overall for benign and cancers separately. For benign masses, up and downgrades will be reported for masses with and without mammograms.

To assess the net effect of downgrades and upgrades, a net gain will be computed in SAS using contrast statements for the ANOVA to determine weight (W) of the malignant outcomes (TP and FN) to determine the value $(A-B+W(C-D))$ that achieves statistical significance, where A, B, C and D are defined as:

- A. Benign Masses correctly downgraded using IUS+OA post
- B. Benign Masses incorrectly upgraded using IUS+OA post
- C. Malignant masses correctly upgraded using IUS+OA post

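### The Protocol scores moves between BI-RADS 2 and 3 in benign masses but not in cancers, and the SAP uses different malignant cells without declaring the change

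*Protocol*

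**What the plan says.** Protocol 2.2 counts a benign mass as correctly downgraded if it moves from IUS BI-RADS 4a to Imagio 2-3, "and from IUS BI-RADS 3 to Imagio (IUS+OA) BI-RADS 2". It counts a benign mass as incorrectly upgraded if it moves from 2-3 to 4-5, or "from IUS BI-RADS 2 to Imagio (IUS+OA) BI-RADS 3-4-5". So the boundary between categories 2 and 3 is scored in both directions for benign masses.

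For cancers, only moves across the line between categories 3 and 4 count. Incorrect downgrades are "the percent of incorrect downgrades for malignant masses from IUS BI-RADS 4-5 to Imagio (IUS+OA) BI-RADS 2-3", and correct upgrades are "the percent of correct upgrades for malignant masses from IUS BI-RADS 2-3 to Imagio (IUS+OA) BI-RADS 4-5". Protocol Table 1 repeats the split, with "BR4a→BR2-3; BR3→BR2" for benign downgrades against "BR4→BR2-3; BR5→BR2-3" for malignant downgrades. Tables 2 and 3 follow the same pattern.

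The SAP (Table 1 in 1.1.7, and 1.1.7.1) has a single downgrade definition, "IUS in BR 4a and IUS+OA post in BR 2-3 or IUS in BR 3 and IUS+OA post in BR 2", and a single upgrade definition. It applies both to benign masses and to cancers. Its net-gain terms C and D are the malignant upgrades and downgrades, and Cohort 2 uses the same definitions. SAP section 2, which lists changes from the Protocol, mentions only the mammogram sampling.

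**The concern.** A move between categories 2 and 3 does not cross the line that separates the malignant cells (2-3 against 4-5), so it leaves sensitivity and specificity at that line unchanged. Scoring it in one diagnosis and not the other lets a change in category habits, unrelated to truth, alter the benign percentages with nothing on the malignant side to set against it. Protocol Table 1 asks for an advantage on benign downgrades and no disadvantage on malignant downgrades. A purely habitual downward shift could appear to meet both.

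This bears on the study's purpose. A benign downgrade advantage is the core of the third illustrative move-forward criterion (Protocol 9.8, item 3), and choosing the pivotal endpoints is a primary objective. In addition, the Protocol and SAP cells give different malignant downgrade counts from the same reads.

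**Working it through.** **Inputs.** From the documents: 75 benign and 45 malignant masses in Cohort 1, 30 malignant masses in Cohort 2, the category cells above, and the net gain A−B+W(C−D). The documents do not give the share of masses in each category or the size of any shift, so those are assumptions below. The plan has no figure of its own for this endpoint to reproduce.

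**Step 1: enumerate the moves (IUS to Imagio).**

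| Move | Protocol, benign | Protocol, cancer | SAP, either diagnosis |
|---|---|---|---|
| 3→2 | correct downgrade | not scored | downgrade |
| 2→3 | incorrect upgrade | not scored | upgrade |
| 4a→2-3 | correct downgrade | incorrect downgrade | downgrade |
| 4b, 4c or 5→2-3 | not scored | incorrect downgrade | not scored |
| 2-3→4-5 | incorrect upgrade | correct upgrade | upgrade |

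The first two rows are the only moves that the Protocol scores in benign masses and not in cancers. Rows one, two and four are where the Protocol and SAP disagree for cancers.

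**Step 2: a relabelling blind to truth.** Let a fraction f of all IUS category 3 masses become category 2, with nothing else moving. Assume 20% of benign and 5% of malignant masses are in category 3, and f = 0.3.
- Benign credit: A = 75 × 0.20 × 0.3 = 4.5.
- Under the Protocol cells B = C = D = 0, so a net gain built from them is +4.5.
- Under the SAP cells D = 45 × 0.05 × 0.3 = 0.675. Net gain at W = 1 is 4.5 − 0.675 = +3.8, and it reaches zero at W = 4.5/0.675 = 6.7.
- With benign shares of 10-40% and malignant shares of 2-10%, the W that cancels the credit runs from 1.7 to 33.
- The reverse shift (2→3), with 20% of benign masses in category 2, gives −4.5 under the Protocol cells.
- Six one-way benign moves by one reader give an exact two-sided McNemar p of 2 × 0.5^6 = 0.031 (descriptive only).

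**Step 3: a latent-score model.** Assume unit-variance scores, benign mean 0, cancer mean 2.0, cutpoints −1.0, −0.2, 0.6, 1.6 and 2.6, and equal discrimination for IUS and Imagio. Only the 2/3 cutpoint moves, up by 0.3 or 0.5 SD.
- No re-scoring noise: benign credit is 75 × [Φ(−0.7) − Φ(−1.0)] = 75 × 0.0833 = 6.2, or 75 × [Φ(−0.5) − Φ(−1.0)] = 75 × 0.1499 = 11.2. Benign upgrades are zero.
- Correlation 0.9 between the two reads: benign downgrades are 11.9 and 15.1, and benign upgrades 6.5 and 5.8. The net is 11.9 − 6.5 = 5.4 and 15.1 − 5.8 = 9.3 per reader.
- Cancers moved 3→2 at correlation 0.9: 0.09 and 0.16 of 45 per reader, of which about 0.03 occur with no shift at all.
- Harder, Cohort 2-like cancers (mean 0.3 to 1.0), no noise: from 30 × [Φ(−1.7) − Φ(−2.0)] = 0.65 to 30 × [Φ(−0.8) − Φ(−1.3)] = 3.5 of 30 per reader. The Protocol cells miss these; the SAP cells count them.

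**The case against.** A reader might infer that the cost in cancers is invisible in this study. The documents do not support that. The SAP definition counts a 3-to-2 move in cancers, in Cohort 1, in Cohort 2 and in net-gain term D.

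A reader might also infer that the net gain is biased under the Protocol. Protocol 1.2 words net gain as new true and false positives and negatives, and a 3-to-2 move creates none of these if both categories count as negative. The bias arises only if the entries in Protocol Table 4 are taken to be the Table 1 cells, which the Protocol does not say.

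Nor is the scoring biased in one fixed direction: an upward shift is penalised just as fully, and nothing in the documents shows which way readers will move. Zero benign upgrades holds only without re-scoring noise. At correlation 0.9 there are about six per reader, though the net credit stays positive.

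The effect on decisions is also limited. The primary endpoint comes from ROC curves of probability-of-malignancy scores, not from these cells. The move-forward criteria are illustrative and judged collectively, and p-values are descriptive. The Protocol evidently sees value in moving a benign mass from 3 to 2, and a separate row keeps that information.

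All these limits stand. Two things survive them: the Protocol's one-sided cells, and an undeclared difference between the documents in both directions.

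**Conclusion.** The point holds for the secondary upgrade and downgrade metrics, for any net gain built from those cells, and for the third illustrative move-forward criterion. Under the Protocol cells, a downward shift of the 2/3 boundary unrelated to truth raises the benign downgrade percentage with no counted malignant cost, and an upward shift is scored as a loss. Accuracy at the 3/4 line is the same in both cases. Sensitivity and specificity at the 2% cutoff do not change if no mass crosses it.

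The net benign credit is about 5.4 to 9.3 of 75 per reader at correlation 0.9 (6.2 to 11.2 without noise). This rests on an assumed latent model and an assumed shift of 0.3 to 0.5 SD. The definitional asymmetry and the Protocol-SAP conflict rest on the text alone.

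**What to change.** Use one set of cells in Protocol 2.2 and Tables 1-3 and in SAP Table 1 and 1.1.7.1.
- For cancers, keep every move from 4-5 to 2-3 and from 2-3 to 4-5, including the moves from 4b, 4c and 5 that the SAP now omits.
- Report 3→2 and 2→3 in their own rows, for benign and malignant masses alike.
- Keep those rows out of the headline downgrade and upgrade percentages, the net gain and the move-forward criterion.
- Do not label a cancer moved from 2 to 3 a correct upgrade, as SAP term C would: it remains below the 3/4 line. Adding 3→2 to the malignant downgrades is not enough by itself, because so few cancers are likely to be in category 3 (in step 2 the net only falls from +4.5 to +3.8 at W = 1).
- Record the change from the Protocol in SAP section 2.

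The cost is a wording change and a few table rows, since BI-RADS is already recorded at each read. The headline benign downgrade percentage may become less favourable to Imagio.

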## 2.3 Exploratory Endpoints

To evaluate the following overall and for individual readers for IUS versus Imagio (IUS+OA):

- Imagio (IUS+OA) feature score distributions for benign versus malignant masses

### 3. BACKGROUND AND RATIONALE

The Imagio Feasibility Study is intended to evaluate if a subsequent pivotal study can be implemented to test prospective hypotheses for pre-specified effectiveness endpoints with an acceptable sample size. The Feasibility Study will be based on ITD masses from the PIONEER Pivotal study to simultaneously reflect the distributions with and without mammograms as well as site CDU BI-RADS scores within benign and malignant masses as strata.

### 4. STUDY DESIGN

This will be a single arm, controlled, blinded, multi-reader, multi-case (MRMC) study using a sequential design. The study will include 5-12 readers depending on qualifications and availability.

Imagio (IUS+OA) Training to be completed prior to any reads taking place. Read 1 is immediately followed by Read 2 within the same read session.

- Read 1 (Control): Mammogram (if available) + History + IUS (stills and videos provided), IUS Probability of Malignancy (POM) and BI-RADS scored and the data form locked.
- Read 2 (Test): Mammogram (if available) + History + IUS (stills and videos provided), and Imagio (IUS+OA) (stills and videos provided). An interim IUS POM and BI-RADS is recorded as well as a combined Imagio (IUS+OA) POM and BI-RADS Pre and Post SenoGram on separate data forms.

Read 1 reflects the information available to a radiologist when evaluating standard ultrasound images, taking under consideration the mass and patient history and assessing mammogram results as available. The History details to be provided are summarized under the Blinding section of the protocol. Read 1 (IUS reads) will serve as the control representing current clinical practice. Read 2 (IUS+OA) will be considered the test read and reflect a pre SenoGram IUS and Imagio (IUS+OA) POM and BI-RADS assessment in addition to a post SenoGram IUS and Imagio (IUS +OA) POM and BI-RADS assessment. Following the display of the SenoGram within the Post SenoGram data form, the IUS and OA feature scores are locked, and the reader is prompted to provide a Post SenoGram POM and BI-RADS. Once the Post SenoGram POM and BI-RADS are provided, the form is locked.

A total of 155 complete read sets from the original PIONEER Intention-to Diagnose (ITD) population will be randomly selected from within the PIONEER Study.

- Comprising the 155 mass read sets, the first cohort will consist of 75 benign and 45 malignant masses (reflecting the same 37.5% prevalence of cancer as for the overall pivotal ITD population), classified by conventional diagnostic ultrasound (CDU) as BI-RADS 3 to 5 to be selected at random in proportion to the original assignment distribution of BI-RADS classifications among subjects in the PIONEER Study. To facilitate the alignment of the PIONEER Pivotal Study data with the Feasibility Study data, the mass image set sampling plan will select a proportion with and without mammograms depending on availability of the mammograms, separately for benign and malignant masses. Cohort 1 will be used for the effectiveness endpoint analyses in support of decision making. The same sampling strategy will be used to ensure a comparable proportion of mass image sets as for the PIONEER Pivotal Study.

- The second cohort consists of 30 additional malignant masses for which 1 or more pivotal study readers scored the mass a false negative during a read from the PIONEER study; this will assess if the excess FN rate observed with OA in the PIONEER study can be reversed.
- The third cohort will consist of five DCIS, lymphoma, or Phyllodes masses; this will assess how these atypical cases will be scored. Since there are so few of these cases, mammogram matching will not be possible.

This evaluation will further achieve the following:

1. The incremental contributions of IUS and Imagio (IUS+OA) by assessing the BI-RADS and POM values at each step in the read order traditionally used in clinical practice.
2. The SenoGram performance versus IUS and versus Imagio (IUS+OA) once IUS + OA features are scored with subset evaluation of the effect of presence or absence of the mammographic data on Senogram performance.

The SenoGram is a classification model that predicts the probability that a lesion is malignant for a given set of reader-assigned feature scores and other relevant data. For this study, the SenoGram will consist of two components, a user interface and a back-end computation engine. The reader will enter feature data into the user interface. When all data has been entered, but prior to a final submission of the data, the user interface will graphically display the model's predicted likelihood of malignancy [not to be confused with POM].

The SenoGram figure will also display threshold lines that correspond to estimated sensitivities of 98%, 98.5%, 99%, and 99.5%, in relationship to the boundaries between BI-RADS categories. If the reader changes a feature score, the graphical display will automatically update with the revised prediction. The reader may optionally modify his or her BI-RADS and POM assignments based on the SenoGram predication; however, there is no requirement to do so. The use of the SenoGram result in decision making will be recorded for each reader for each image mass set evaluated. The SenoGram is trained on cases not selected for any Cohort of this study.

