1.1. Statistical and Analytical Plans

1.1.1. Definitions and General Considerations for Data Analysis

1. All calculations will be performed in a GCP-compliant environment using SAS statistical software, version 9.2 or later, StatXact, version 10 or later or OR-DBM MRMC (2.5) or later.
2. This Statistical Analysis Plan (SAP) is based on Clinical Trial Protocol Imagio Feasibility MRMC Study of Optoacoustic Images vs. Imagio Ultrasound to Guide Decision to Biopsy, September 24/November 1, 2018 – Version 3.0.
3. This study is a single arm, controlled, blinded, multi-reader, multi-case (MRMC) study using a sequential design.
4. This feasibility study will be registered at clinicaltrials.gov.
5. There will be up to 12 independent readers to evaluate images using standardized equipment at American College of Radiology (ACR).
6. All readers will read all images utilizing (IUS) and before (IUS+OA pre) and after the SenoGram (SG) prompt (IUS+OA post); prior to all image reads, all readers will have access to mammography images and a clinical history as collected in PIONEER.
7. A total of 155 complete read sets from the original PIONEER Intention-to-Diagnose (ITD) population will be randomly selected from within the PIONEER Study. Only once mass is to be selected per PIONEER subject.
 - Cohort 1 will consist of 75 benign and 45 malignant masses classified by CDU as BI-RADS 3 to 5 selected at random in proportion to the original distribution of Bi-RADS classifications among subjects in the PIONEER Study. To facilitate the alignment of the PIONEER Pivotal Study data with the Feasibility Study data, the mass image set sampling plan will select a proportion with and without mammograms for benign masses. [Note: mammograms were present for nearly all malignant masses.]
 - Cohort 2 will consist of 30 malignant masses with at least one false negative read from the PIONEER study to assess if the excess FN rate observed with OA in the PIONEER study can be reversed. The same proportional sampling strategy with respect to CDU Bi-RADS will be used. Cohort 3 will consist of five DCIS, lymphoma, or phyllodes masses; this will assess if these atypical cases do not introduce FNs or FPs. [Note: Due to the small size, Cohort 3 results will be listed only and not be summarized.]
8. Cohort data will not be combined across cohorts.

9. To assess intermediate performance an interim analysis is planned after each reader has completed at least 72 Cohort 1 masses.

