10. The primary endpoint is to evaluate the gain in specificity at fixed sensitivity for IUS+OA post vs IUS; IUS+OA pre-will be compared to IUS and IUS+OA post.
11. There are no formal hypothesis tests for this Feasibility Study; this study will be used to inform Seno on the design and sample size of a subsequent pivotal study.
12. Feasibility Study data will not be used for registration purposes.
13. Feasibility Study data will not be combined with the subsequent pivotal study but will be used to determine effect sizes to power the subsequent pivotal study.

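### Read 2 always follows Read 1 on the same mass, and no SAP contrast can separate a second-look effect from the effect of OA, although the protocol records an interim IUS score that the SAP never uses

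*Protocol*

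**What the plan says.** Protocol section 4 fixes the order: "Read 1 is immediately followed by Read 2 within the same read session". It names the comparator: "Read 1 (IUS reads) will serve as the control representing current clinical practice". The Read 1 form is locked once IUS POM and BI-RADS are entered. Read 2 shows the mammogram (if available), history and IUS again, and adds the OA stills and videos. For Read 2 the protocol states: "An interim IUS POM and BI-RADS is recorded", alongside the combined scores before and after the SenoGram. The same section also mentions an IUS assessment after the SenoGram, so IUS may be scored up to three times per mass.

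Among the aims in section 4 is to evaluate "The incremental contributions of IUS and Imagio (IUS+OA) by assessing the BI-RADS and POM values at each step in the read order". No endpoint in protocol section 2 names the interim IUS score.

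The SAP works with three scores. Section 1.1.1 item 6: "All readers will read all images utilizing (IUS) and before (IUS+OA pre) and after the SenoGram (SG) prompt (IUS+OA post"). Item 10: "The primary endpoint is to evaluate the gain in specificity at fixed sensitivity for IUS+OA post vs IUS". Table 1 and section 1.1.7.1 add IUS+OA pre vs IUS and IUS+OA post vs IUS+OA pre. The SAP does not mention Read 1, Read 2 or a second IUS score, and does not say which IUS score its label IUS denotes. SAP section 2, on changes to the planned analyses, lists only the mammogram sampling change.

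**The concern.** IUS+OA pre differs from Read 1 IUS in two ways: OA has been added, and the reader has looked at the same IUS and mammogram a second time. The order is never reversed and there is no interval between the reads, so the design does not balance the second factor. The SAP has no contrast that estimates it. A score that might do so is collected and left unanalysed.

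Attribution matters because the study exists to produce effect sizes. Protocol section 9.1 uses them to judge whether a pivotal study is justified and, if so, to size it; SAP section 1.1.1 item 13 repeats the sizing use. If part of the observed gain came from re-reading, the team would want to know that before choosing the pivotal endpoint and read design.

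The control is also undefined in the SAP. The protocol points to Read 1, but an analyst holding two or three IUS scores per mass has no SAP sentence to follow.

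**Working it through.** **Stated figures.** The plan gives no power, effect size or second-look figure to reproduce. Its counts are consistent: 45/(75+45) = 37.5%, and 75+45+30+5 = 155.

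**What the planned contrasts identify.** For any one accuracy measure, let S1 be Read 1 IUS, S2 the Read 2 interim IUS, and Pre and Post the two combined scores. Then

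Post − S1 = (Post − Pre) + (Pre − S2) + (S2 − S1).

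The SAP estimates Post − S1, Pre − S1 and Post − Pre. Post − Pre isolates the SenoGram step and contains no Read 1 score. Pre − S1 is the sum of the last two terms, and nothing in the SAP splits it. Using S2 would.

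**When the split has the intended meaning.** If S2 is scored before OA is displayed, S2 − S1 is the second-look effect and Pre − S2 is the OA increment net of it. If OA is already visible, S2 may reflect OA. Then S2 − S1 may include part of the OA effect, and Pre − S2 may understate OA. Protocol section 4 places S2 within Read 2, where OA is provided, and does not give its timing. The workflow and interface figures are not shown in the text reviewed, and the Independent Review Charter is not part of it, so the timing cannot be settled here.

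**Scale at a fixed POM cutoff (assumption).** If a second look alone moves 2 to 5 of 75 benign masses to negative for a reader, the shift is 2/75 = 2.7% to 5/75 = 6.7%. This applies to the secondary analysis at the 2% POM cutoff.

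**Why that scale does not transfer to the primary endpoint.** At fixed sensitivity the threshold follows the malignant scores. With 45 malignant masses, 0.98 × 45 = 44.1, so a reader's empirical 98% point lies between 44/45 = 97.8% and 45/45 = 100%. The lowest malignant scores set it. A second look that lowers benign and malignant POMs alike need not change specificity there. Specificity rises only if re-reading separates the two groups better, and could fall if it separates them less well.

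**Consequence for sizing, if the pivotal study targets the OA increment (assumption).** The paired-proportion formula is

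n = [z₀.₉₇₅√ψ + z₀.₈₀√(ψ − d²)]² / d²,

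with two-sided 5% error and 80% power (protocol section 9.8, move forward criteria). The gains and the discordance ψ = 0.20 are assumed. The formula treats each benign mass as one paired comparison, so it is not an MRMC calculation.

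| Apparent gain | Second-look part | OA part d | n for apparent gain | n for OA part | Power of planned n for OA part |
|---|---|---|---|---|---|
| 10 points | 2 points | 8 points | 155 | 243 | 61% |
| 10 points | 5 points | 5 points | 155 | 626 | 28% |
| 15 points | 2 points | 13 points | 68 | 91 | 68% |
| 15 points | 5 points | 10 points | 68 | 155 | 45% |

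First row: for d = 0.10, (1.960 × 0.4472 + 0.842 × 0.4359)²/0.01 gives 155. For d = 0.08, (1.960 × 0.4472 + 0.842 × 0.4400)²/0.0064 gives 243. With ψ = 0.30 the ratios of n are almost unchanged (1.56 and 4.02 for 10 points; 1.33 and 2.27 for 15 points).

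**The case against.** The sequential design is deliberate. The protocol ties it to "by assessing the BI-RADS and POM values at each step in the read order traditionally used in clinical practice", and the steps named in that aim, IUS and Imagio (IUS+OA), are both analysed. No protocol endpoint uses the interim score, so the SAP omits no promised endpoint. P-values are descriptive, there are no formal hypotheses, and the data are not for registration. All of this stands. It is why the design and the Read 1 control should be left alone and the request kept to supportive analyses.

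A reader might infer more than the documents support:

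- That the primary gain is inflated. No second-look effect is shown, and its direction is unknown.
- That the gain is credited to OA alone. The primary contrast is IUS+OA post vs IUS, so the credit goes to OA plus the SenoGram. Post vs pre already isolates the SenoGram step.
- That the pivotal study would be undersized. If it keeps the same read sequence and estimand, the effect including any second look is the right one to power on. The table above applies only if it targets the OA increment. A different read design would also bring the second look into play. The documents state neither.
- That the interim score is a clean second-look control. Its timing relative to OA display is not stated.

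**Conclusion.** The point holds as a limit on attribution. The order is fixed, an interim IUS score is recorded in Read 2, and neither SAP contrast with IUS (post vs IUS, primary; pre vs IUS) can separate a second look from OA. This rests on reading the SAP's IUS as Read 1, which the protocol supports but the SAP does not state. If the SAP meant the interim score, the second-look point would fall away and the control would no longer match the protocol, so the definition is needed either way.

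The size of any bias is unknown. At fixed sensitivity it inflates the gain only if re-reading improves discrimination, and it affects pivotal sizing only if the pivotal study targets the OA increment or reads in a different design. The addition is still worth making, because it is inexpensive and the study's purpose is to estimate effect sizes.

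**What to change.** 1. State in SAP section 1.1.1 that IUS means the locked Read 1 score, and keep it as the control for the primary contrast.
2. State whether the interim IUS is scored before the OA images are displayed.
3. Add to SAP Table 1, as supportive descriptive contrasts for Cohort 1, interim IUS vs Read 1 IUS and IUS+OA pre vs interim IUS. Report both for specificity at 98% sensitivity, and for sensitivity and specificity at the 2% POM cutoff.
4. Interpret them as the second-look effect and the OA increment net of second look only if the interim score precedes OA display. Otherwise report them with the caveat that the interim score may already reflect OA and the OA increment may be understated.

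Cost: two extra descriptive contrasts on scores that the protocol already collects. No new reads are needed, and because the SAP makes no multiplicity adjustment there is no error-rate cost. The sponsor should accept in advance that the effect attributed to OA may turn out smaller.
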